3.1.1.3 Protocol

This is a prospective, randomized and blind pilot study.

The FriWalk validation as a therapeutic tool will be carried out in two clinical scenarios, one of them in geriatric acute care and the other in Orthogeriatrics Unit, because people usually use the walker in these units. On the other hand, the FriWalk validation as a diagnostic tool (SPPB and gait speed) will be carried out in Acute Care Geriatrics Unit, in those patients who have been recruited to FriWalk validation as a therapeutic tool.

The duration of the pilot will be one year, we will have two FriWalk during pilot. Recruitment time will be six months from the start of the pilot study.

Regarding the number of patients who will participate in the study, as FriWalk is a new technologic tool, which going to be included in model care in elderly people, we do not have previous data to evaluate the effect of the walker in clinical scenario. Hence, correct sample size cannot be calculated. So, we propose developing a pilot study in which all patients who meet inclusion and exclusion criteria and sign the inform consent will be included. The pilot study will last a year.

Patients' evaluations, in therapeutic tool scenario, will be carried out during hospitalization (in admission and discharge), one month after discharge, three months after discharge and six months after discharge. The last evaluation will be done by phone. A block randomization will be performed to ensure a balance between the control group and the intervention group in each setting. The block size is 4 (2 for control group and 2 for intervention group). In order to perform the randomization, we will always need that one of the FriWalk is free.

In the FriWalk validation as a diagnostic tool, the tests will be performed once there will not be a further follow-up.

In table 1 we will find described the professionals that participate in the pilot study as well as their responsibilities.

Table 1. Professionals.

PROFESSIONALS.		
RESPONSABLE:	COMPETENCES:	
Clinical researcher.	 Pre-screening and screening phases: check that patients meet inclusion and exclusion criteria. Give information to patients and caregivers about the pilot study and provide informed consent. The clinical researcher will carry out the evaluations during hospitalization, in discharge, and afterwards (one month after discharge and three months after discharge). Validation of the FriWalk as a diagnostic tool. 	
Physician.	 Pre-screening phase: the physician along with the clinical researcher will made a pre- selection of patients that could be participants in the pilot study. 	
Technical support.	- The technical support will develop training sessions about walker use. In addition, the walker maintenance will be carried out.	
Occupational Therapist.	 Exercises prescription. Validation of the FriWalk as diagnostic tool in Geriatrics Acute Care Unit. 	
FIB-HUG Professionals.	- They will perform the analysis data.	

A. VALIDATION OF THE FRIWALK AS A THERAPEUTIC TOOL:

Patients' selection will be made within 48 hours of initial hospital admission in the Geriatric Acute Care Unit, and in the Orthogeriatrics Unit after the stand permission by traumatology. These patients will be identified in both units through the admission list. Then physician and clinical researcher will check those participants who fulfil the inclusion and exclusion criteria. Next the participants will sign the informed consent and later the will be assigned by using a randomization process (through the www.randomizerd.org tool) to the control group or to the intervention group.

- **Control group**: the participants will receive the usual intervention, including rehabilitation programs if the participants need it during hospitalization.
- Intervention group: the participants will receive the usual intervention, including rehabilitation programs if the participants need it. In addition, we will provide them with the FriWalk as well as the exercises recommendations which prescribed by their physician and the Occupational Therapist.

Patients in the intervention group, who are hospitalized in Geriatric Acute Care or in Orthogeriatrics Unit, will dispose of the FriWalk at the time they have received authorization for walking by their doctor in Acute Care Unit, or for standing in Orthogeriatrics Unit until their discharge respectively.

The evaluations will be the same in both groups. When clinical researcher detects any alterations in the tests or questionnaires which might condition the patient's clinical management, the physician will be informed to take the appropriate measurements.

For both groups, data will be collected in five different moments; when patients' admission, at discharge, one month, three and six months after discharge.

In table 2 is describe pilot study in Geriatric Acute Care Unit and Orthogeriatrics Unit.

PHASE I: PRE-SCREENING.		
RESPONSABLE:	DESCRIPTION:	
Clinical researcher. Physician.	Clinical researcher and physician will make an initial selection based on admission list (Orthogeriatrics Unit and Geriatrics Acute Care Unit). They will have to check that patients meet the inclusion and exclusion criteria a priori.	
PHASE II: SCREENIN	G AND RECRUIMENT.	
RESPONSABLE:	DESCRIPTION:	
Clinical researcher.	 Over pre-selected patients will be carried out different actions: Patients meet inclusion and exclusion criteria. Provide information about pilot study. If patients agree to participate in pilot study, informed consent will be provided and if they agree, then they will sign it. 	
PHASE III: RANDOMIZATION.		
RESPONSABLE:	DESCRIPTION:	
Person who does not participate in pilot study.	If patients agree to participate in the pilot study and sign the informed consent, they will be randomized and consequently assigned to control group or intervention group.	
PHASE IV: FIRST V	/ISIT (ADMISSION).	
RESPONSABLE:	DESCRIPTION:	
Clinical researcher. Occupational Therapist.	 Clinical researcher will carry out a patient examination composed of different tests and evaluations. Demographic and clinical data. Gait speed in 6 meters (Graham et al. 2008). SPPB (Short Physical Performance Battery) (Freiberger et al. 2012). Barthel Índex (Barthel and Mahoney 1965). Lawton and Brody (Lawton and Brody 1969). Confussion Assessment Method (Vasunilashorn et al. 2016). Semantic and Phonologic fluency (Mirra et al. 1991). MMSE (Folstein, Folstein, and McHugh 1975). Clock Drawing Test (Shulman 2000). 	

Table 2. Pilot study phases as therapeutic tool.

PHASE V RESPONSABLE: Technical support.	 Yesavage (Greenberg 2012). EuroQL-5D (Group 1990). Visual Analogue Scale for pain (only in Orthogeriatric Unit). Occupational Therapist will prescribe the physical exercises that patients should do. TRAINING. DESCRIPTION: After randomization, patients assigned to the
	intervention group, as well as their family and caregivers, will receive a training session about how to use the system.
PHASE VI:	FOLLOW-UP.
RESPONSABLE:	DESCRIPTION:
Technical support. Physician. Occupational Therapist.	During hospitalization, the technical support team will visit patient if he will need help for using the FriWalk. The physician and the Occupational Therapist will do the clinical follow-up.
PASE VII:	DISCHARGE.
RESPONSABLE:	DESCRIPCIÓN:
Clinical researcher.	 New evaluation will be carried out at discharge moment with different tests and evaluations from admission. Demographic and clinical data. Gait speed (6 meters). SPPB (Short Physical Performance Battery). Barthel Índex. Lawton and Brody. Confusion Assessment Method. Semantic and Phonologic fluency. MMSE. Clock Drawing Test. Yesavage. EuroQL-5D. Visual Analogue Scale for pain (only in Orthogeriatric Unit). Length of admission. Adherence to treatment. We obtain this information by the FriWalk in the intervention group, and by questionnaires in the control group. Assistant level at discharge. System _Usability Test (intervention group).
PHASE VIII: VISIT 1 MC	ONTH AFTER DISCHARGE.
RESPONSABLE:	DESCRIPTION:
Clinical researcher.	 New evaluation will be carried out one month after discharge. Different test will be performed. Demographic and clinical data. Gait speed (6 meters). SPPB (Short Physical Performance Battery).

	/
	 Barthel Índex. Lawton and Brody. Confusion Assessment Method. Semantic and Phonologic fluency. MMSE. Clock Drawing Test. Yesavage.
	 EuroQL-5D. Visual Analogue Scale for pain (only in Orthogeriatric Unit). New admissions. Emergency visits.
	 Admission days in Emergency. Primary care visits Falls. Mortality. Assistance level at month 1.
PHASE IX: VISIT 3 MONT	
RESPONSABLE:	DESCRIPTION:
Clinical researcher.	 Last evaluation will be carried out. Demographic and clinical data. Gait speed (6 meters). SPPB (Short Physical Performance Battery). Barthel Índex. Lawton and Brody. Confusion Assessment Method. Semantic and Phonologic fluency. MMSE. Clock Drawing Test. Yesavage. EuroQL-5D. Visual Analogue Scale for pain (only in Orthogeriatric Unit). New admissions. Emergency visits. Admission days in Emergency. Primary care visits Falls. Mortality. Assistance level at month 1.
PHASE X: TELEPHON EVALUATIO	
RESPONSABLE:	DESCRIPTION:
Clinical researcher.	 We will make a call, 6 months after discharge: Barthel Índex. EuroQL. Mortality. Assistance level at month 1.
PHASE XI: DA	TA ANALYSIS.
RESPONSABLE:	DESCRIPTION:
FIB-HUG professionals.	At the end of the study, data analysis will be carried out using the information stored during the pilot study. Then, conclusions will be drawn about the use of the walker.

B. VALIDATION OF THE FRIWALK AS A DIAGNOSTIC TOOL.

Patients selected to validate the FriWalk as a diagnostic tool will be those who have been selected for therapeutic validation in Acute Care Geriatrics Unit setting.

Patients will have to perform the Short Physical Performance Battery (SPPB) and the gait speed (6 meters). Then, we will compare data acquired by FriWalk and data acquired by a traditional method.

Table 3 describes the pilot study in Acute Care Geriatrics Unit as a diagnostic tool.

PHASE I: PRE-SCREENING.		
RESPONSABLE:	DESCRIPTION:	
Clinical researcher. Occupational Therapist.	Initially, clinical researcher and occupational therapist will make an initial selection among patients who have been admitted in Acute Care Geriatrics Units. These patients must meet a priori the inclusion and exclusion criteria.	
FASE II: SCREENING	AND RECRUIMENT.	
RESPONSABLE:	DESCRIPTION:	
Clinical researcher. Occupational Therapist.	 Different actions will be carried out in selected patients. Check inclusion and exclusion criteria. Provide information about the study. If patients agree, the informed consent will be provided and if they agree they will have to sign it. 	
PHASE I	II: SPPB.	
RESPONSABLE:	DESCRIPTION:	
Clinical researcher. Technical support. Occupational Therapist.	SPPB will be performed in Acute Care Geriatrics Unit. Clinical researcher will use the FriWalk and Occupational Therapist will measure this test by using a traditional method.	
PHASE IV: (GAIT SPEED.	
RESPONSABLE:	DESCRIPTION:	
Clinical researcher. Technical support. Occupational Therapist.	Gait speed in 6 meters will be performed in Acute Care Geriatrics Unit. Clinical researcher will use the FriWalk to measure gait speed and Occupational Therapist will do it through traditional method.	
PHASE V: FEEDBACK COL	LECTION OF PHYSICIANS.	
RESPONSABLE.	DESCRIPTION.	
Clinical researcher.	Three test will be realized: - System Usability test. - Acceptability and satisfaction test.	
PHASE VI: DA	TA ANALYSIS.	
RESPONSABLE:	DESCRIPTION:	
FIB-HUG personal.	At the end of the study, data collected will be analysed. Then, conclusions will be drawn about the use of the Walker as a diagnostic tool.	

Table 3. Pilot Study phases as diagnostic tool.

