3.1.1.2 Participants

The FriWalk validation as a therapeutic tool will be carried out in two different and independent clinical scenarios (two settings), one of them will be Geriatric Acute Care Unit and the other will be Orthogeriatrics Unit. We will select patients over 75 years old in both scenarios. For the validation of the FriWalk as a diagnostic tool, we will recruit patients over 75 years old only in Geriatric Acute Care Unit.

As it is a novel technological tool in the care model of elderly patients, we do not have previous data to evaluate the effect of an intelligent walker in the clinical scenarios. Therefore, we will develop a pilot in which we will include all patients who meet the eligibility criteria and sign the informed consent for a stipulated time of one year.

INCLUSION AND EXCLUSION CRITERIA:

A. GERIATRIC ACUTE CARE UNIT:

- Inclusion criteria:
 - \circ Patients' \geq 75 years old.
 - Supervision during hospitalization by caregivers or family.
 - Ability to walk with or without aid prior to hospitalization.
- Exclusion criteria:
 - $\circ \quad \geq 48h \text{ of stay in the hospital.}$
 - $\circ \quad \mbox{Inability to understand and use the FriWalk}.$
 - o Illness that impedes carrying out the prescribed therapy.

- Acute myocardial infarction in the last 3 months.
- Instable cardiovascular disease.
- Terminal illness.
- Other pathologies involving clinical instability.
- Functional impairment established (Barthel Index < 40).
- Precedent of alcohol and/or drug abuse.
- Psychiatric disorders (Schizophrenia and psychotics disorders.
- Participation in any other clinical study.

B. ORTHOGERIATRICS UNIT:

Inclusion criteria:

0

- Patients' \geq 75 years old.
- Hip fracture surgery with permission to stand during hospitalisation.
- Supervision during hospitalization by caregivers or family.
- Ability to walk with or without aid prior to hospitalization.
- Exclusion criteria:
 - $\circ \geq 48h$ after surgery intervention.
 - Inability to understand and use the FriWalk.
 - Illness that impedes carrying out the prescribed therapy.
 - Acute myocardial infarction in the last 3 months.
 - Instable cardiovascular disease.
 - Terminal illness.
 - Other pathologies involving clinical instability.
 - \circ Functional impairment established (Barthel Index < 40).
 - History of alcohol and/or drug abuse.
 - Psychiatric disorders (Schizophrenia and psychotics disorders.
 - Participation in any other clinical study.

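### A single block size of 4, printed in the protocol, lets a recruiter who tracks allocations deduce on average up to one third of them, an avoidable selection-bias risk

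*Protocol*

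**What the plan says.** Protocol section 3.1.1.3 sets the scheme: "A block randomization will be performed to ensure a balance between the control group and the intervention group in each setting". The next sentence fixes it: "The block size is 4 (2 for control group and 2 for intervention group". No varying block size and no other safeguard against prediction is described.

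The same section labels the trial: "This is a prospective, randomized and blind pilot study". It does not say who is blinded or how. Controls receive usual care. For the intervention group it adds: "In addition, we will provide them with the FriWalk". No sham or comparator walker is described.

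Table 1 gives the clinical researcher these duties: "Pre-screening and screening phases: check that patients meet inclusion and exclusion criteria", and "Give information to patients and caregivers about the pilot study and provide informed consent". The same role carries out the evaluations in hospital, at discharge, and one and three months later. At discharge (Table 2, Phase VII) that researcher gives the usability test to the intervention group only, and takes adherence from the walker in one arm and from questionnaires in the other.

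Randomisation follows consent and is assigned to an outsider (Table 2, Phase III): "Person who does not participate in pilot study". There are two walkers, and one must be free before a patient can be randomised.

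The exclusion criteria in section 3.1.1.2 include "Inability to understand and use the FriWalk" and an open category of other conditions causing clinical instability.

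**The concern.** An outside randomiser hides the allocation list. That does not hide the next allocation from someone who knows the block size and what has already been assigned. With blocks of 4, once two patients of a block are in the same arm, or once three are in, the rest of that block is settled.

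Three features make this usable here. The block size stands in the document that recruiting staff work from; section 3.1.2 makes the clinical researcher responsible for running the study according to it. Past assignments can be learned, because a robotic walker on the ward is conspicuous and the researcher's own discharge assessment differs by arm. And entry leaves room for judgement: whether a patient can understand and use the device, whether the patient is clinically unstable, and when and how to seek consent.

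If the expected arm influences those decisions, even without intent, the arms may differ in prognosis from the start. The primary aims in section 3.1.1.1 are about functional outcome, and section 3.1.4 sets a 0.05 significance level, so comparability of the arms matters even though the study is called a pilot.

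**Working it through.** The protocol states no predictability, power or sample-size figure, so there is none to reproduce.

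**Inputs.** Block size 4, 2:2, within each unit (section 3.1.1.3). Assumption: the recruiter knows every earlier allocation in that unit before the next enrolment and knows where each block starts.

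**Allocations known with certainty.** There are C(4,2) = 6 equally likely blocks. In 2 of them (AABB, BBAA) the last two places are settled; in the other 4 only the last is.

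- Mean settled per block: (2×2 + 4×1)/6 = 8/6 = 1.333.
- Share: 1.333/4 = 33.3%.
- By position: 0, 0, 1/3, 1.

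**Incomplete last block.** The first two places of a block are never certain.

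- 10 patients in a unit: 2 × 1.333/10 = 26.7%.
- 30 patients: 7 × 1.333/30 = 31.1%.
- 20 or 40 patients: 33.3%.

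**Best guess** (choose the arm with more places left). Probability correct by position:

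- 1st: 1/2.
- 2nd: 2/3.
- 3rd: 1/3 × 1 + 2/3 × 1/2 = 2/3.
- 4th: 1.
- Mean: (1/2 + 2/3 + 2/3 + 1)/4 = 17/24 = 70.8%, against 50% without prediction.

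**Alternatives.** Larger fixed blocks were enumerated in the same way. Mixed sizes were simulated (4,000 runs of 40 allocations, sizes drawn with equal probability) for an observer who knows the set of sizes but not their order.

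| Scheme | Certain | Best guess correct | Largest imbalance in a unit |
|---|---|---|---|
| Fixed 4 | 33.3% | 70.8% | 2 |
| Fixed 6 | 25% | 68.3% | 3 |
| Fixed 8 | 20% | 66.6% | 4 |
| Random 4/6 | about 6% | about 69% | 3 |
| Random 4/6/8 | about 2% | about 68% | 4 |

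The largest imbalance is half the largest block, reached when recruitment stops midway through it.

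**Device constraint.** In simulated sequences of 20 allocations (an illustrative length), a run of three or more consecutive FriWalk assignments occurs in just under half with fixed 4, about 64% with 4/6 and about 70% with 4/6/8. Runs of five or more cannot occur with fixed 4 and occur in about 4% with 4/6/8.

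**The case against.** The strongest reply is that the protocol already restricts steering. An outside person randomises after consent. Candidates come from the admission list. A physician checks eligibility together with the researcher. All eligible, consenting patients are to be included, and the 48-hour limits leave little time to hold a patient back for a preferred slot. These points stand and make steering harder. They do not remove the discretion in the judgement-based exclusions or in the consent approach, and none of them prevents deduction from past allocations.

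A reader might infer that the recruiter necessarily sees every allocation as it happens. The protocol does not say so. Technical support trains the intervention patients, the physician and occupational therapist follow them in hospital, and the walker is handed over only after authorisation to walk or stand. The researcher's first written arm-specific task is at discharge. Earlier knowledge through the ward is likely but inferred.

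A reader might also infer a bias that no analysis could remove. That goes too far: gait speed, SPPB, Barthel, Lawton and MMSE are measured at admission in both arms, so selection on measured function can be seen and adjusted for. The protection is incomplete, because those tests come after randomisation (Phase IV follows Phase III), are done by the same researcher, and do not capture everything that drives a judgement of fitness.

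Finally, varying the blocks leaves most of the guessing advantage: it falls from 20.8 points above chance to just under 18 with 4/6/8. That is correct, and is why the block size should also be kept from the recruiting staff and the order of steps documented.

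**Conclusion.** The point holds as an avoidable risk that the protocol itself creates by fixing and printing one block size. A recruiter who tracks allocations in a unit could know on average up to one third of them with certainty over complete blocks, fewer in a small unit with an incomplete last block, and guess about 71% correctly. These figures are exact given the stated scheme; they rest on the assumption of full and timely knowledge of earlier allocations, which the procedures make possible but do not establish.

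It would be tempting to conclude that the bias could be as large as a plausible treatment effect. The documents do not support that: section 3.1.1.3 says the sample size cannot be calculated, and no effect size or standard deviation is given, so predictability cannot be converted into bias on any outcome. Nor do they show that steering would occur. Describing the study as blind does not answer the point, because no blinded party is named and the described procedures reveal the arm to the researcher.

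The change is worth making because it is cheap and removes nearly all certain foreknowledge.

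**What to change.** 1. Have the independent randomiser use randomly varying block sizes, separately for each unit: for example 4 and 6, or 4, 6 and 8.
2. Delete the block size from the protocol, say only that permuted blocks of varying size are used within each unit, and hold the sizes in a document closed to recruiting staff.
3. Time-stamp eligibility and consent in the eCRF before each allocation is released. Table 2 already puts consent before randomisation; the time-stamp makes that order verifiable.

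Cost: one setting in the allocation list, one sentence changed and one eCRF field. There are two statistical and practical downsides. Imbalance within a unit can reach 3 (4/6) or 4 (4/6/8) instead of 2. Longer runs of FriWalk assignments become more likely, which could mean more waiting for a device and more patients passing the 48-hour limit. The chosen sizes should therefore be checked against the rule that one of the two walkers must be free. The 4/6 mix gives up a little of the gain in unpredictability for shorter runs and a smaller possible imbalance.

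### The trial is called blind, but its outcome assessor has discharge tasks that reveal the arm, and Table 2 places randomisation before the baseline assessment

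*Protocol*

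**What the plan says.** **Label.** Section 3.1.1.3 opens with "This is a prospective, randomized and blind pilot study". It does not say which role is masked or how.

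**Order.** The text on the therapeutic validation reads "Next the participants will sign the informed consent and later the will be assigned by using a randomization process". Table 2 agrees. Phase II ends with consent; in Phase III "they will be randomized and consequently assigned to control group or intervention group"; Phase IV is the admission visit, where "Clinical researcher will carry out a patient examination composed of different tests and evaluations", including gait speed, SPPB, Barthel, cognition and mood. Nowhere is the admission examination placed before allocation.

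**Who allocates.** Phase III gives this to a "Person who does not participate in pilot study". In section 3.1.3.1, assigning a participant to a group in the eCRF is reserved for the administrator.

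**Who scores.** Table 1: "The clinical researcher will carry out the evaluations during hospitalization, in discharge, and afterwards", the later visits being months 1 and 3. Phase X of Table 2 gives the month 6 call to the same role.

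**What else that role does at discharge.** Phase VII lists only the clinical researcher. Its contents include adherence, taken from the FriWalk in the intervention arm and from questionnaires in the control arm, and a test marked "Usability Test (intervention group" only.

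**The concern.** Two of the three primary goals in section 3.1.1.1 are less functional decline in hospital and earlier recovery afterwards. No instrument is named as the primary variable for either. The natural candidates are SPPB, gait speed and Barthel, all scored by this one role. These scales leave room for encouragement and judgement, so an assessor who knows the arm can shift them without intending to. Patients handle the device themselves and cannot be masked, so the assessor is where masking would protect the functional results.

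A baseline taken after allocation opens a second route. If the assessor knew the arm by then, a shift in the admission score would enter change from admission in full, and would enter a baseline-adjusted analysis in part. A reader who sees the word blind would assume that neither route exists.

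**Working it through.** The protocol states no sample size, SD or effect, so there is no figure to reproduce. The main check is a trace of who does what and when.

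**Step 1: exposure of the assessor by visit** (Tables 1 and 2)

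| Visit | Scored by | Can the assessor know the arm? |
|---|---|---|
| Admission (Phase IV, after Phase III) | Clinical researcher | Possible, not shown |
| Discharge (Phase VII) | Clinical researcher | Likely, unless function is tested first with no FriWalk in view; neither is required |
| Months 1 and 3 (Phases VIII, IX) | Clinical researcher | Yes, learned at discharge |
| Month 6 call (Phase X; Barthel and EuroQol, no SPPB or gait speed) | Clinical researcher | Yes, learned at discharge |

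The discharge entry reflects that intervention patients keep the FriWalk until they leave. Table 5 describes adherence simply as a set of questions. Even if one form served both arms, the usability test alone would reveal the arm.

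At admission there is a possible cue. The occupational therapist shares Phase IV and prescribes exercises in it, while section 3.1.1.3 describes prescribed exercise recommendations only under the intervention group.

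**Step 2: how a shift enters the estimate.** Let the assessor favour one arm by b at baseline and by d at follow-up, in SD units with equal SDs at both visits.

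- Change score: bias = d − b.
- Baseline-adjusted analysis with correlation ρ: bias = d − ρb.

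If only the baseline is shifted, by b = 0.2, the change-score estimate moves by 0.20. The adjusted estimate moves by 0.5 × 0.2 = 0.10 to 0.9 × 0.2 = 0.18 (ρ assumed 0.5 to 0.9). If d = b, the change score is unbiased. If the baseline was in fact masked, b = 0 and the whole of d remains.

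**Step 3: illustration of size.** Assume a true effect of 0, a two-sided 5% test, a net SPPB shift of b points, a change SD of 2 or 3, and n = 15 or 25 per arm. All of these except the 0.05 level are assumptions; section 3.1.4 gives 0.05 without stating sidedness.

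SE = SD × √(2/n), z = b/SE, false-positive rate = P(|Z + z| > 1.96).

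Example: SD 2, n = 25 gives SE = 2 × √(2/25) = 0.566. With b = 0.5, z = 0.884 and the rate is 14.3%.

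| SD | n per arm | Net shift 0.5 point | Net shift 1 point |
|---|---|---|---|
| 2 | 15 | 10.5% | 27.8% |
| 2 | 25 | 14.3% | 42.4% |
| 3 | 15 | 7.4% | 15.0% |
| 3 | 25 | 9.1% | 21.8% |

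For a fixed shift the inflation grows with n, so recruiting more patients does not cure it.

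**The case against.** **Safeguards around allocation.** Someone outside the study randomises, the eCRF group assignment is closed to the researcher, and device training (Phase V) follows the baseline. The two revealing tasks come at discharge, so they cannot affect that same patient's admission scores. This stands. A reader might infer from the phase order that the baseline is already biased; the documents do not show that the researcher is told the arm before Phase IV. The safeguards cover the act of allocation, however, and do nothing for the later visits.

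**Order within the discharge visit.** SPPB and gait speed are listed before adherence and usability and could be scored first. That is true, but the list is not stated to be a sequence, and it would not help months 1, 3 and 6.

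**Cancellation.** An assessor equally generous to one arm at both visits leaves the change score unbiased. This also stands, so the percentages above apply only to a net shift.

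**The label might refer to someone else.** A reader might conclude that no role could be blind. That goes too far: the FIB-HUG professionals in Table 1 only analyse data and could work with coded arms. The protocol does not say that this is what the label means.

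**The diagnostic sub-study.** It is tempting to add that "Clinical researcher will use the FriWalk to measure gait speed" in Table 3. That does not reveal the arm, because the sub-study takes acute-care patients from the therapeutic trial with no restriction by arm. It forms no part of this point.

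**Conclusion.** The point holds in this form. The blind label is undefined, and the protocol's own division of tasks defeats masking of the outcome assessor. That is certain for months 1, 3 and 6 as the tasks are assigned, and likely at discharge. At admission, the order of Phases III and IV leaves an avoidable opening, with the exercise prescription as a possible cue, but no exposure is demonstrated.

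The size of any bias cannot be derived from the document. The ranges of about 7–14% and 15–42% rest on assumed SDs, sample sizes and net shifts, and show only that modest shifts matter in a small trial. That SPPB, gait speed and Barthel would carry the primary therapeutic comparison is an inference, since no instrument is named.

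Visit order, task assignment and the blinding label belong to the protocol. A statistical analysis plan could not restore masking once data are collected, so the change should be made before enrolment.

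**What to change.** 1. **Reorder Phases III and IV.** Obtain consent, confirm that a FriWalk is free, complete the admission assessment, and only then randomise or release the allocation. The occupational therapist's prescription should follow, out of the researcher's sight.
2. **Separate the revealing tasks from scoring.** In Phase VII, give adherence (both arms) and the usability test to existing staff who do not score outcomes. Technical support is a candidate, since it already trains the intervention patients and so knows their arm. It is not listed in Phase VII, so this would be a new duty there. Keep allocation from the clinical researcher. Do the discharge and follow-up function tests for the therapeutic comparison with no FriWalk in view. The Table 3 sessions need no change for this purpose.
3. **Correct the label.** Replace blind with *open-label with outcome assessor masked to allocation*, or with *open-label* if masking cannot be kept.

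The cost is protocol wording and a modest re-assignment of tasks. An occasional patient will be assessed at baseline and then not randomised, for example if the FriWalk is no longer free.
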